To compare two loading protocols using the new implant (NobelParallel™ CC) in posterior healed sites in two treatment arms: one in which the implant will be immediately provisionalized at the time of surgery, and another where the provisional crown will be delivered 3 months after the surgical procedure.

STUDY DESIGN AND STATISTICAL PROCEDURES OVERVIEW

This is a non-inferiority study of 12-month duration comparing the two treatment arms described above. Eligible patients with edentulous spaces at the maxillary or mandibular premolar/molar areas will be randomized to either an immediate provisionalization or a delayed provisionalization treatment arm. Patients in both treatment arms will receive their final fixed restoration at 4 months after surgery. The primary outcome of the study will be the radiographically assessed alveolar bone level change at the mesial and distal surface of the implant at 6 and 12 months after surgical placement. Secondary outcomes will include implant survival,

volumetric soft tissue changes, peri-implant probing depth, and implant stability by resonance frequency analysis.

POWER CALCULATIONS AND STATISTICAL ANALYSIS

Determination of sample size was based on anticipated differences in the primary outcome between the two treatment arms at 6 months (change in alveolar level from the time of implant placement). Based on similar data published in the literature (Esposito et al., 2013), we calculated with 1 mm bone remodeling in one treatment arm, and 1.5 mm bone remodeling in the second arm (i.e., expected mean difference between the two arms amounting to 0.5 mm). With a common standard deviation in both arms of 0.6 mm, the two-tailed effect size for a Student t-test (Cohen's d) amounts to 0.8333 mm. For an alpha error of 0.05 and power of 0.80, a total of 48 individuals in both arms is required for a two-tailed hypothesis. Thus, our plan is to enroll 50 individuals into the study.

Differences in the primary and secondary outcomes between the two treatment arms will be calculated using t-test for unmatched samples, after checking for data normality. Additional analyses will include regression models in which insertion torque (a measure of primary implant stability at the time of surgical placement) will be also used as a covariate along with treatment group allocation.

STUDY PROCEDURES

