Eligible participants (i.e., adults ≥ 18 years old in need of a dental implant at a posterior maxillary or mandibular region) who have been referred for dental implant treatment at the Clinics of the College of Dental Medicine will be approached by the study investigators and the aims of the study will be explained. Signed informed consent will be obtained.

All patients will be referred for limited field cone beam computer tomography to assess presence of adequate bone volume at the area of interest, according to standard clinic protocol. Alginate impressions will be obtained to fabricate diagnostic stone casts. A vacuum-formed stent will be manufactured in the laboratory to offer fixed reference points for longitudinal probing measurements, and a radiographic stent using polyvinyl siloxane interocclusal record material will allow standardized positioning of the radiographic holder to obtain periapical radiographs with the same projection geometry.

At the day of surgery (baseline), a computer-generated sequence will assign patients to either the one-stage or the two-stage treatment arm. In both arms, the implant will be placed flush with the bone crest, after flap elevation, according to standard treatment protocol. A periapical radiograph will be obtained immediately after completion of surgery.

Patients in the one-stage group will receive a temporary acrylic crown manufactured chair-side at the same visit. Care will be taken to relieve the crown from occlusal and laterotrusive contacts. The distance from the soft tissue margin to the occlusal stent will be measured using a periodontal probe at six sites around the implant (mesiobuccal, midbuccal, distobuccal, mesiolingual, midlingual and distolingual) at the time of post-surgical follow-up, 1-2 weeks after surgery.

At three months after implant surgery, patients in the two-stage group will have the implant uncovered after punching the oral mucosa, according to standard protocol. An acrylic temporary crown will be delivered. Soft tissue margin assessments measurements will be carried out, as described above, will be carried out at the time of post-surgical follow-up, 1-2 weeks after surgery.

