At four months after implant surgery, patients in both arms will have a final fixture level impression according to standard protocol for fabrication of the final implant supported restoration (a full contour Zirconia abutment crown with an angulated screw channel), which will be delivered approximately 2 weeks later. Resonance frequency analysis measurements will be obtained to determine implant stability using an Ostell™ device. After delivery of the final restoration, a periapical radiograph will be obtained, soft tissue margin measurements will be carried out as described above, and peri-implant probing depths will be assessed at the same six sites. An alginate impression will also be obtained to produce a stone cast to be used in volumetric measurements.

At seven months after implant surgery, patients in both treatment groups will return for a follow up visit to reinforce oral hygiene and will receive oral prophylaxis.

At twelve months after implant surgery, patients in both treatment groups will return for a follow up visit to reinforce oral hygiene and to receive oral prophylaxis. Resonance frequency analysis measurements will be obtained to determine implant stability using an Ostell™ device. A periapical radiograph will be obtained, soft tissue margin measurements will be carried out as described above, and probing depths will be assessed at the same six sites around the implant. An impression will be obtained to produce a cast to be used in volumetric measurements. The 12-month examination will conclude the study visits.

Research procedures

1. Radiographic measurements of alveolar bone level mesial and distal to the implant (at baseline, four months and 12 months) will be carried out using the MIPACS software. The implant platform will be the reference point. Note that although the measurements will be carried out for the purposes of the study, periapical radiographs after completed surgery, at the time of delivery of the final restoration, and at 12-months post-surgery are standard protocol in implant dentistry. Thus, the study does not require any additional exposure to radiation beyond what is considered the standard of care.

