Potential participants will be approached by the study investigators and the scope and the procedures of the study will be thoroughly explained. Eligible individuals willing to participate will provide informed consent.

CONFIDENTIALITY OF THE DATA

Participants will be assigned individual study numbers that will be used to link all collected study data. All endpoint devices used for data collection will be password-protected and encrypted. PHI/PII data and all other study data will be stored in a secure, certified database. The following individuals/ institutions/ representatives will have access to the records: the Principal Investigator and co-investigators, the FDA, the Department of Human Health and Human Services, the Columbia University/New York Presbyterian Hospital, and the Institutional Review Board. Absolute confidentiality cannot be guaranteed because of potential need to share this information with the above parties. Only aggregate findings of this study will be published.

POTENTIAL CONFLICT OF INTEREST

The study is an investigator-initiated randomized controlled trial, where the Principal Investigator serves as the Sponsor-Investigator. The study is partially supported by a grant provided by the implant manufacturer (Nobel Biocare). None of the investigators have any financial interest in the company or have served as paid consultants.

LOCATION OF THE STUDY

All study procedures will take place at the Clinics for Post-doctoral Periodontics and Post-doctoral Prosthodontics, College of Dental Medicine, Columbia University Medical Center, Vanderbilt Clinic, 9th floor.

POTENTIAL RISKS

Study related risks: The overall success of dental implants exceeds 95%. Risks associated with the study are identical to those associated with surgical implant placement and include soreness, discomfort, pain, infection, nerve damage and implant failure.

Protection against risks: Implants will be placed and restored by post-doctoral residents who are proficient in the surgical and restorative aspects of implant dentistry, under faculty supervision. Patients will receive post-operative antibiotic and analgesic coverage, according to standard clinical protocol.

POTENTIAL BENEFITS

Patients will have the costs associated with implant surgery and provisional restoration waived, as these will be covered by funds provided by the implant manufacturer (NobelBiocare).

ALTERNATIVE THERAPIES

- 1) not to replace the missing tooth

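### The primary t-test is valid but makes no use of jaw or premolar/molar site, and no text keeps the arm from the operator until the implant is seated and torque recorded

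*Combined protocol and SAP*

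**What the plan says.** The section on power calculations and statistical analysis sets one test for all outcomes: "Differences in the primary and secondary outcomes between the two treatment arms will be calculated using t-test for unmatched samples", after a check of normality. Additional regression models follow, in which "insertion torque (a measure of primary implant stability at the time of surgical placement) will be also used as a covariate" together with treatment group. Torque is the only covariate named.

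Jaw and tooth position enter as a description of who is eligible. The design overview says: "Eligible patients with edentulous spaces at the maxillary or mandibular premolar/molar areas will be randomized". The Study Procedures section adds that the area is imaged by cone beam CT before surgery. Neither factor is named as a stratification factor or a model term.

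On allocation, Study Procedures says: "At the day of surgery (baseline), a computer-generated sequence will assign patients to either the one-stage or the two-stage treatment arm". Placement is described next, with one rule for both arms: "In both arms, the implant will be placed flush with the bone crest, after flap elevation, according to standard treatment protocol". A periapical radiograph is taken straight after surgery. Then: "Patients in the one-stage group will receive a temporary acrylic crown manufactured chair-side at the same visit". Under Research procedures, item 1, bone level is measured on the radiograph and "The implant platform will be the reference point". Potential Risks says that implants are placed by post-doctoral "residents who are proficient in the surgical and restorative aspects of implant dentistry, under faculty supervision". No section mentions allocation concealment, operator blinding, or holding the assignment until the implant is in place.

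**The concern.** There are two linked issues.

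**Precision.** If jaw or site explains part of the bone-level change, the unadjusted test reports a wider interval than the same 50 patients could give. Interval width matters in a trial described as non-inferiority, with 50 patients and no stated allowance for dropout.

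**What follows assignment.** Jaw and site cannot be affected by the arm. Torque can be, if the operator knows the arm when placing the implant. A model that adjusts for torque would then condition on something the assignment may have influenced. Seating could also differ by arm and affect later remodeling, and such a difference could not be separated from the effect of the loading protocol.

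**Working it through.** **Inputs.** From the power section: difference 0.5 mm (1.0 against 1.5 mm), common SD 0.6 mm, two-sided alpha 0.05, power 0.80, 48 required, 50 to enroll. Assumed: 1:1 allocation (no ratio is stated), no losses, and R² for jaw and site together over a range from 0 to 0.25. The SD is the plan's 6-month planning value. The 0.5 mm is its expected difference, not a non-inferiority margin; none is stated.

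**1. The plan's own figure.** SE = 0.6 × √(2/n), with power from the noncentral t on 2n − 2 df.
- n = 24 per arm: SE = 0.1732 mm, power 0.807. The stated 48 reproduces.
- n = 25 per arm: SE = 0.1697 mm, power 0.823, half-width 2.0106 × 0.1697 = 0.341 mm.

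**2. Adjusting for jaw and site (two terms, df = 50 − 4 = 46).** When stratification balances both factors, SE = 0.6 × √(1 − R²) × √(2/25). Without stratification, chance imbalance inflates the variance by about 47/45 on average. The t quantile is 2.0129.

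| R² | Stratified: half-width (mm) | Stratified: power | Unstratified: half-width (mm) |
|---|---|---|---|
| 0 | 0.342 | 0.822 | 0.349 |
| 0.02 | 0.338 | 0.830 | 0.346 |
| 0.09 | 0.326 | 0.856 | 0.333 |
| 0.25 | 0.296 | 0.915 | 0.302 |

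Example, stratified at R² = 0.09: 0.6 × √0.91 = 0.5724; × √0.08 = 0.1619; × 2.0129 = 0.326 mm.

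**3. Break-even.** Adjustment narrows the interval when R² exceeds:
- stratified: 1 − (2.0106/2.0129)² = 0.002;
- unstratified: 1 − (2.0106/2.0129)² × 45/47 = 0.045.

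**4. Stratifying without adjusting.** This was simulated with 50 patients, permuted blocks of 4 within jaw-by-site strata, half the sites maxillary and half molar, R² split equally between the two factors, and 30,000 trials per setting. The plain t-test becomes conservative: type I error is about 0.042 at R² = 0.09 and 0.026 at 0.25. Its power is 0.834 and 0.852, against 0.855 and 0.913 when adjusted. Stratification and adjustment therefore belong together.

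**5. Order of events.** In the text the order is assignment, placement, radiograph, then the one-stage crown at the same visit. Torque arises at placement. Nothing in that order requires the arm to be known before the crown is made, so assignment could be opened after seating. The documents give no basis for putting a figure on an operator effect.

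**The case against.** The strongest reply is that the first part is a preference about efficiency. A reader might infer that omitting jaw and site biases the comparison or inflates type I error. It does neither: under randomization the t-test is valid, and chance imbalance is already in its standard error. With half the sites maxillary, an imbalance in jaw of 20 percentage points or more has probability 20.3% under simple allocation, or 25.8% with arms fixed at 25/25. Those figures describe lost precision and no further harm. Nothing in the documents says that jaw or site predicts bone change, so the gain is hypothetical, and without stratification adjustment makes the interval wider at R² = 0.02. The power figures concern detecting 0.5 mm, not showing non-inferiority. All of this stands.

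On the second part, a reader might infer that the operator knows the arm before seating the implant. The documents say only that assignment falls on the day of surgery; the order of sentences is suggestive, and what remains is an omission. A reader might also infer that platform position feeds directly into the primary outcome. The outcome is change since placement, measured from a radiograph taken right after surgery, so an offset in seating depth is largely subtracted. The shared flush-placement rule and faculty supervision limit differences further. They do not exclude an effect of seating on later remodeling.

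Finally, torque is used only in additional analyses, and the plural wording about regression models does not exclude other covariates. It is the only named covariate, not demonstrably the only one planned.

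**Conclusion.** The point holds as two inexpensive improvements, not as an error in the primary test or the sample size. With stratification by both factors and adjustment, power falls by about 0.001 if jaw and site explain nothing. It rises by about 3 points at R² = 0.09 (0.823 to 0.856) and 9 at R² = 0.25 (0.823 to 0.915). These figures rest on an assumed R², the 6-month SD of 0.6 mm, 25 analyzed per arm and no losses. The operator route is possible and unaddressed. It is not shown to occur, it is limited for the primary change outcome, and it is not quantified. It bears most directly on how the torque-adjusted model can be read.

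**What to change.** **(a) Stratify and adjust.** Stratify the computer-generated sequence by jaw and, if practicable, by site. Pre-specify: *Primary analysis: linear regression of bone-level change (one value per implant, at the primary time point) on arm, jaw (maxilla/mandible) and site (premolar/molar); the arm difference is reported with its 95% CI. The unmatched t-test is a sensitivity analysis.* The sponsor must supply the time point and the rule for combining mesial and distal values, because the design overview names 6 and 12 months while Research procedures, item 1, measures at baseline, four and 12.

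Cost: a stratified sequence and a short analysis paragraph, with no extra patients or visits. If jaw and site explain nothing, the loss in power is about 0.001 (stratified by both), 0.01 (by jaw only) or 0.02 (unstratified). If stratification is not possible, adjustment pays only above an R² of about 0.045.

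**(b) State when the arm is revealed.** For example: *The assignment is opened only after the implant is seated and insertion torque is recorded.* This changes the timing of disclosure within the same visit. The downside is that provisional-crown materials must be ready for every patient. If it is not adopted, label the torque-adjusted model exploratory, because torque may then depend on the arm.

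### The 12-month bone-level t-test ignores the earlier follow-up film of patients lost in between; one repeated-measures model of both films would use it at almost no cost.

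*Combined protocol and SAP*

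**What the plan says.** The Study Design section names bone-level change at 6 and 12 months as the primary outcome of a 12-month non-inferiority study. The section on power and statistical analysis gives the comparison: "Differences in the primary and secondary outcomes between the two treatment arms will be calculated using t-test for unmatched samples", after a normality check. The additional regression models contain arm and insertion torque.

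Item 1 under Research procedures lists the bone-level readings: "Radiographic measurements of alveolar bone level mesial and distal to the implant (at baseline, four months and 12 months". Each patient who completes the study therefore has a baseline film and two follow-up films. Study Procedures places the first follow-up film after delivery of the final restoration, about two weeks after the four-month impression.

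On size, the plan works with "expected mean difference between the two arms amounting to 0.5 mm", a common SD of 0.6 mm, and the settings "For an alpha error of 0.05 and power of 0.80". It concludes that "a total of 48 individuals in both arms is required for a two-tailed hypothesis", and then: "Thus, our plan is to enroll 50 individuals into the study". The calculation is tied to the 6-month comparison. The plan states no dropout rate, analysis population, method for missing films, or rule for the bone level of a failed implant.

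**The concern.** An unmatched t-test takes one value per patient. Run at month 12, it can use only patients with a 12-month film. A patient who had the first follow-up film and then left contributes nothing, although the early bone-level change is likely to predict much of the later one.

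Two things are at stake. The first is precision: information already collected is thrown away. The second is bias. The t-test is valid under loss only if, within each arm, having a 12-month film is unrelated to bone level. If patients with more early bone loss leave one arm more readily, the remaining patients flatter that arm. If it were the immediate arm, the error would favour a non-inferiority conclusion.

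The point concerns patients who leave or miss a film. Failed implants are a separate matter.

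**Working it through.** **Inputs.** From the documents: difference 0.5 mm, SD 0.6 mm, two-sided alpha 0.05, power 0.80, 48 required, 50 enrolled. Assumed, because the documents give no figures: equal arms, 20% of 12-month films missing for the precision check and about 15% for the bias check, correlation 0.5 to 0.8 between early and 12-month change, and SD 0.6 mm at both times.

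**Step 1: the plan's own figure.** Effect size d = 0.5/0.6 = 0.8333. For a two-sided t-test, the noncentral-t calculation gives 23.60 per arm, so 24 per arm and 48 in total. The stated 48 reproduces.

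**Step 2: power by analysable number.** With arms a and b, the noncentrality is d × √(ab/(a+b)) on a+b−2 degrees of freedom. At 25 per arm it is 0.8333 × √12.5 = 2.946.

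| Analysable | Lost of 50 | Power |
|---|---|---|
| 50 | 0 | 82.3% |
| 48 | 2 | 80.7% |
| 47 | 3 | 79.8% |
| 45 | 5 (10%) | 78.0% |
| 43 | 7 (14%) | 76.0% |
| 40 | 10 (20%) | about 73% |

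These are powers to detect a 0.5 mm difference. They carry over to month 12 only if the same difference and SD hold there.

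**Step 3: precision when 20% of 12-month films are missing at random.** Let n = 50 patients have the early film and c = 40 also have the 12-month film. In units of the 12-month variance, the complete-case estimate has variance proportional to 1/c. In large samples, the maximum-likelihood estimate using the early film has variance proportional to (1−ρ²)/c + ρ²/n. Its reciprocal is the equivalent number of patients.

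- Complete cases: 40.
- ρ = 0.7: 0.51/40 + 0.49/50 = 0.01275 + 0.00980 = 0.02255, equivalent to 44.3 patients.
- ρ = 0.8: 0.36/40 + 0.64/50 = 0.00900 + 0.01280 = 0.02180, equivalent to 45.9 patients.

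Simulation with 25 per arm, which allows for estimating the slope, gives 39 to 40 for the t-test, about 43 to 44 for the joint model at ρ = 0.7, and about 46 at ρ = 0.8.

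**Step 4: bias in an assumed adverse case.** In the immediate arm, suppose a patient misses the 12-month film with probability 45% if early loss is more than 0.5 SD above the mean, and 2% otherwise. In the delayed arm, suppose a flat 15%.

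- A standard normal exceeds 0.5 with probability 0.3085, and its density there is 0.3521.
- Missing in the immediate arm: 0.45 × 0.3085 + 0.02 × 0.6915 = 0.153.
- Mean early score among those remaining: (0.55 − 0.98) × 0.3521/(1 − 0.153) = −0.179 SD, or −0.179 × 0.6 = −0.107 mm.
- Carried to month 12 by ρ: 0.5 × 0.107 = 0.054 mm, 0.7 × 0.107 = 0.075 mm, 0.8 × 0.107 = 0.086 mm, all in favour of the immediate arm.

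Simulation of the same case gives 0.05 to 0.09 mm for the t-test and about zero for the joint model. For scale, the standard error of the difference at 21 per arm is 0.6 × √(2/21) = 0.185 mm.

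**The case against.** The strongest case against is that little is shown to be broken, and much of it stands.

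- **Power.** A reader might infer that ordinary dropout takes the trial below its stated 80% at month 12. The documents do not support that. The 80% belongs to 6 months, no 12-month power is stated, and 50 patients give 82%. At 5% loss (47.5 on average) power is still about 80%; at 10% it is 78%. Any shortfall rests on an assumed loss above about 5%.
- **Bias.** A reader might infer that the t-test will favour the immediate arm. The figure comes from a constructed pattern, dependent on early loss in one arm only, and is under half a standard error. The joint model's near-zero bias follows because missingness was made to depend only on the early film.
- **The remedy does not replace lost patients.** At 20% missing and ρ = 0.7, about 43 equivalent patients give 76% power, still below 80%. Keeping 48 analysable would take 48/0.9, or 54 enrolled, at 10% loss, and 48/0.8 = 60 at 20%.
- **Early losses.** The first follow-up film follows delivery of a restoration that patients pay for themselves. Anyone who leaves before then has no follow-up film, and the model recovers nothing for them.
- **The 50.** A reader might infer that patients found unsuitable on the cone beam scan, which follows consent in the text, count against the 50. The plan randomises eligible patients on the day of surgery and does not say that enrolment means consent, so this is speculation.

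It can also be said that complete-case analysis is never stated. That is true. It follows from a t-test with no rule for missing films, and no other reading is offered.

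What the objections do not answer is that the joint model uses data already scheduled, gives the same 12-month difference as the t-test when no film is missing, and needs a weaker assumption when some are.

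**Conclusion.** The point holds as a worthwhile, inexpensive improvement to the analysis. It does not show a design failure.

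The gain is about 3 to 6 patients' worth of precision at month 12 if 20% of films are missing at random and the correlation is 0.7 to 0.8. It also protects against a bias of about 0.05 to 0.09 mm in one adverse case, at most roughly a sixth of the 0.5 mm design difference. Loss rates, correlations and dropout pattern are all assumptions, since the plan gives none.

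The power figures are secondary. They concern detecting a difference, so they are not power for non-inferiority. The plan gives no non-inferiority margin, and without one the bias cannot be judged against the trial's own decision rule.

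**What to change.** Replace the separate t-tests on bone-level change with one likelihood-based repeated-measures model:

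- outcomes: change from baseline at both follow-up films, one value per patient per film;
- terms: arm, time and arm-by-time, with unstructured covariance;
- patients: all randomised patients with at least one follow-up film;
- result: the 12-month arm difference and its confidence interval, read from this model.

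State how missing films are assumed to arise, and give failed implants their own rule so that their later bone levels are not treated as missing at random.

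The cost is a change of analysis wording and slightly more analysis work, with no new visits, films or patients. The model assumes that missingness is explained by arm and the earlier film. It does nothing for patients lost before the first follow-up film, and it is not a substitute for a loss allowance if the sponsor wants 80% power kept at a stated loss rate.
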